	
response (CR) and partial response (PR).
 
 
OS is defined as the number of days from the date of treatment initiation (i.e., Cycle 1 Day 1) to the date of death from any cause. In the event that no death is documented prior to study termination or analysis cutoff, OS will be censored at the last date the patient is known to be alive.
 
 
In addition, relationships between antitumor activity, PDn markers, exploratory biomarkers, and drug exposure levels will be explored.
	
treatment. In the event that no disease progression or death is documented prior to study termination, analysis cutoff, or the start of confounding anticancer therapy, these endpoints will be censored at the date of last available tumor assessment.
 
 
OS is defined as the number of days from the date of treatment initiation (i.e., Cycle 1 Day 1) to the date of death from any cause and will be calculated for all patients who receive at least one dose of treatment. In the event that no death is documented prior to study termination or analysis cutoff, OS will be censored at the last date the patient is known to be alive.
 
	

Attachment 1: Schedule of Study Assessments
	
Not included in Amendment 1
	
MRI brain with contrast
	
Language added to include MRI of the brain for all cohort 4 patients to determine baseline status

Attachment 1: Schedule of Study Assessments
	
Explanation of Superscripts 3. Vital sign measurements include temperature, pulse, respiratory rate
	
Explanation of Superscripts 3. Vital sign measurements include temperature, pulse, respiratory rate
	
Updated the vital sign measurement schedule

Section(s)	Amendment 1	Amendment 2	Rationale
	and resting systolic and diastolic blood pressure. On the day of nivolumab infusion, vital signs will be obtained pre-infusion, every 15 minutes during the infusion, at the end of infusion, and 15, 30, 60 minutes after completion of the infusion. Vital signs should be collected $\pm$ 5 minutes from the scheduled times note above.	and resting systolic and diastolic blood pressure. On the day of nivolumab infusion, vital signs will be obtained pre-infusion and within 30 minutes of the end of the infusion. Vital signs should be collected $\pm$ 5 minutes from the scheduled times noted above	
Attachment 1 : Schedule of Study Assessments	Explanation of Superscripts 4. To be performed in duplicate and should be performed approximately 5 min apart	Explanation of Superscripts 4. Duplicate ECGs are NOT required.	Removed requirement for duplicated ECGs
Attachment 1 : Schedule of Study Assessments	Explanation of Superscripts 10. Nivolumab dosing will take place on D1 and D15 of every cycle. Infusion of nivolumab will precede CB-839 dosing and PK analysis on C1D1 and C1D15.	Explanation of Superscripts 10. Nivolumab dosing will take place on D1 and D15 of every cycle. On PK days (C1D1, C1D15, C2D1 and C3D1), patients will bring their morning dose of CB-839 to clinic. Pre-dose procedures must be completed, then the patient will eat breakfast and take their CB-839 dose and then the infusion of nivolumab will be administered. Cohort 6 patients have the option to add Nivolumab at progression on CB-839 monotherapy.	Clarified dosing procedures during PK days

Section(s)	Amendment 1	Amendment 2	Rationale

Attachment 1: Schedule of Study Assessments
	
Explanation of Superscripts 11. CB-839 is given BID on C1D1, C1D15, C2D1 and C3D1, patients should be instructed not to eat breakfast prior to their clinic visit. The morning dose of CB-839 will be administered during the clinic visit after all pre-dosing procedures and predose PK blood sampling, has occurred. On C2D1 and C3D1 and CB-839 may be administered prior to the nivolumab infusion, but pre-dose procedures must be completed prior to CB-839.
	
Explanation of Superscripts 11. CB-839 is given BID with food approximately 12 hours apart. On PK days (C1D1, C1D15, C2D1 and C3D1), patients will bring their morning dose of CB-839 to clinic. Pre-dose procedures must be completed, then the patient will eat breakfast and take their CB-839 dose and then the infusion of nivolumab will be administered.
	
Clarified dosing procedures during PK days


Attachment 1: Schedule of Study Assessments
	
Explanation of Superscripts 12. Whenever possible, imaging should be done at the same institution/ facility and with the same modality which will be used to measure response during the patient’s participation in the study. The redacted copies of the reports will be submitted and the scans must be sent to a reader for exploratory analyses. If available, 1-3 redacted scan reports for scans that occurred prior to screening will be requested.
	
Explanation of Superscripts 12. Whenever possible, imaging should be done at the same institution/ facility and with the same modality which will be used to measure response during the patient’s participation in the study. The redacted copies of the reports will be submitted and the scans must be sent to a reader for exploratory analyses. All scans from the immediate prior line of therapy will be requested for Cohorts 2, 4, and 5.
	
Addition of archival scan collection for Cohorts 2, 4, and 5.

Section(s)	Amendment 1	Amendment 2	Rationale

Attachment 1: Schedule of Study Assessments
	
Explanation of Superscripts
 
Not in Amendment 1
	
Explanation of Superscripts
 
13. For Cohort 4 only: baseline radiographic imaging of disease will also occur within 7 days prior to C1D1 unless the screening assessment meets the criteria described in Section 10.1.
	
Updated the baseline radiographic imaging requirement for Cohort 4

Attachment 1: Schedule of Study Assessments
	
Explanation of Superscripts
 
14. Completed approximately every 8 weeks per RECIST 1.1. Evaluations may occur more frequently as clinically indicated.
	
Explanation of Superscripts
 
14. Completed approximately every 8 weeks from Cycle 1 Day 1 per RECIST 1.1. Studies should include chest/abdomen/pelvis and all other known areas of disease. Evaluations may occur more frequently as clinically indicated. Patients with an objective response (CR or PR) should have repeat imaging at least 4 weeks later to confirm the objective response. In addition, patients with progressive disease should undergo a second scan at least 4 weeks later to confirm progression.
	
Clarified the timing and procedures of follow up scans


Attachment 1: Schedule of Study Assessments
	
Explanation of Superscripts
 
Not in Amendment 1
	
Explanation of Superscripts
 
16. To be included for patients with known CNS disease.
	
Additional MRI requirement for patients with known CNS disease

Section(s)	Amendment 1	Amendment 2	Rationale

Attachment 1: Schedule of Study Assessments
	
Explanation of Superscripts 16. A baseline tumor biopsy is required for all patients enrolled in Phase 2. Postdose tumor biopsies are required for all patients in Cohorts 2, 4, and 5 and should be collected on Cycle 2 Day 1 (<math>\pm</math> 1 week). Coagulation tests must be performed and evaluated within 24 hr prior to all biopsy procedures. Instructions on biopsy processing can be found in the Laboratory Manual.
	
Explanation of Superscripts 18. A baseline tumor biopsy is required for all patients enrolled in Phase 2. Postdose tumor biopsies are required for all patients in Cohorts 2 and 5 and should be collected on Cycle 2 Day 1 (<math>\pm</math> 1 week). Predose and postdose biopsies will be collected for the first 30 patients enrolled into stage 2 of Cohort 4. For all subsequently enrolled patients, only a pre-dose biopsy will be collected. Coagulation tests must be performed and evaluated within 72 to 24 hr prior to all biopsy procedures. Instructions on biopsy processing can be found in the Laboratory Manual.
	
Updated biopsy assessment for Cohort 4 and increased the window for coagulation testing prior to biopsy procedure

Attachment 1: Pharmacokinetic and Biomarkers Sampling Schedule
	
Not in Amendment 1
	
Phase 1 and Phase 2 Biomarker: TCR^6
 
 
• Cycle 1 Day 1: 3 mL
 
• Cycle 1 Day 15: 3 mL
 
• Cycle 3 Day 1: 3 mL
 
• Total sample: 9 mL
 
	
Addition of collection time points for TCR analysis

Section(s)	Amendment 1	Amendment 2	Rationale
Attachment 3: Clinical Laboratory Tests	Serum Chemistry-Full Metabolic Panel (Peripheral Blood Sample) with additional analytes	Serum Chemistry-Full Metabolic Panel (Peripheral Blood Sample) with additional analytes  Thyroid Stimulating Hormone (TSH)	Updated serum chemistry to remove magnesium, phosphorus, uric acid, direct bilirubin, and thyroid function tests and add thyroid stimulating hormone test.
Attachment 3: Clinical Laboratory Tests	Urinalysis	Urinalysis • Only institutional standard urinalysis is required	Updated urinalysis to require only institutional standards
Attachment 5: iRECIST: modified RECIST 1.1 for immune-based therapeutics	Attachment 5: Immune Related RECIST Criteria (based on RECIST 1.1)	Attachment 5: iRECIST: modified RECIST 1.1 for immune-based therapeutics	For consistency across all sites, the updated iRECIST guidelines will be implemented

### 3 LIST OF ABBREVIATIONS

[figure not shown]
Abbreviation	Definition
AE	Adverse event
BID	Twice daily
CI	Confidence interval
CNS	Central nervous system
CR	Complete response
CTCAE	Common Terminology Criteria for Adverse Events
DOR	Duration of Response
ECG	Electrocardiogram
EOT	End of Treatment
FDA	Food and Drug Administration
hr	Hour or hours
IRC	Independent radiology committee
MedDRA	Medical Dictionary for Drug Regulatory Activities
MTD	Maximum tolerated dose
NCI	National Cancer Institute
ORR	Overall response rate
OS	Overall Survival
PD	Progressive Disease
PFS	Progression Free Survival
PK	Pharmacokinetic(s)
PO	Per os (administered by mouth)
PR	Partial response
PT	Preferred term
QTcF	Corrected QT interval, Fridericia's formula
RECIST	Response Evaluation Criteria in Solid Tumors
RP2D	Recommended Phase 2 Dose
SAE	Serious adverse event
SAP	Statistical analysis plan
SD	Stable disease
SOC	System organ class
TEAE	Treatment-emergent adverse event

## 4 INTRODUCTION

The statistical analysis plan (SAP) provides details of the planned analyses and statistical methods for the study CX-839-004 (A Phase 1/2 Study of the Safety, Pharmacokinetics, and Pharmacodynamics of the Glutaminase Inhibitor CB-839 in Combination with Nivolumab in Patients with Advanced/Metastatic Melanoma, Renal Cell Carcinoma and Non-Small Cell Lung Cancer). The background and rationale for the study can be found in the study protocol.

## 5 STUDY DESIGN

Protocol CX-839-004 is a Phase 1/2 open-label study of the combination of CB-839 with nivolumab in patients with advanced/metastatic ccRCC, MEL, and NSCLC, as well as CB-839 monotherapy in patients with advanced/metastatic MEL. Sequential dose escalation of CB-839 with full dose nivolumab (CB-Nivo) will take place in patients with advanced ccRCC, advanced/metastatic MEL, or metastatic NSCLC. Subsequently, multiple disease-specific single-arm cohorts will be enrolled in which CB-839 will be administered in combination with the full approved dose of nivolumab. CB-839 will be administered at the RP2D established in dose escalation. Patients in dose escalation must be eligible for one of the dose expansion cohorts. CB-839 monotherapy will be administered at the previously established monotherapy RP2D of 800 mg PO BID (twice daily).

Dose escalation will use a 3+3 design and will enroll cohorts of 3-5 patients with advanced ccRCC, advanced/ metastatic MEL, or metastatic NSCLC at escalating doses as outlined in Table 6.3-1 in the protocol amendment 2. Patients will receive escalating doses of CB-839 in combination with the FDA-approved anti-PD-1 agent nivolumab. Nivolumab will be administered at the FDA-approved dose of 240 mg every 2 weeks without adjustment for body weight.

Dose limiting toxicities (DLTs) observed in Cycle 1 (first 28 days of dosing) will be used to determine escalation to the next dose level. In general, patients who experience a DLT will not receive further treatment with the study drugs.

The Maximum Tolerated Dose (MTD) is defined as the highest dose level with no more than 1 DLT reported in 6 DLT-evaluable patients.

During dose escalation, patients must receive at least 75% of the planned CB-839 administrations and both doses of nivolumab in the first 28-day treatment cycle to be considered evaluable for DLT, unless the patient has a DLT or has the study drug held for an adverse event (AE) that may herald a DLT.

The starting dose of CB-839 will be 600 mg BID. The first dose of CB-839 will be administered in the morning with breakfast. The second dose will be administered in the evening with a meal approximately 12 hr ( $\pm$  2 hr) after the morning dose.

Dose escalation will continue until identification of a MTD or up to a maximum dose of 800 mg orally BID, thus the maximum dose will be 800 mg BID. Up to 6 additional patients may be enrolled to a dose escalation cohort in order to generate additional safety, pharmacokinetic (PK), and biomarker data.

The Recommended Phase 2 Dose (RP2D) of CB-Nivo will be selected based on the clinical data and will not exceed the MTD. To further characterize safety, tolerability, and efficacy, additional patients will be enrolled at the RP2D in specific cohorts in Phase 2 – Cohort Expansion. Please refer to Section 6.3.2 in the protocol for details.

## **5.1 Protocol Synopsis**

Please refer to protocol amendment 2 dated 14 Nov 2017 (1). The Schedule of Assessments is in Appendix A: Schedule of Study Assessments.

## **5.2 Study Endpoints**

### **5.2.1 Efficacy Endpoints**

#### **5.2.1.1 Primary Efficacy Endpoint**

The primary efficacy endpoint is the confirmed overall response rate (ORR) and duration of response (DOR) of patients treated with CB-839 in combination with nivolumab. Overall Response Rate is defined as the percentage of patients with complete response (CR) or partial response (PR) per Response Evaluation Criteria in Solid Tumors (RECIST) v1.1. DOR is defined as the time between the first

documentation of a PR or a CR per RECIST v1.1 to the first documentation of progressive disease (PD) or death. For all cohorts, the primary end point is investigator assessed.

### 5.2.1.2 *Secondary Efficacy Endpoints*

The secondary efficacy endpoints are:

- Progression free survival (PFS) of patients treated with CB-839 plus nivolumab. PFS is defined as time from first dose date to the earlier of either progression of disease per RECIST v1.1 or death from any cause.
- Overall survival (OS) of patients treated with CB-839 plus nivolumab. Overall Survival is assessed by time from first dose date to death due to any cause.

### 5.2.2 *Safety Endpoints*

The safety endpoints are:

- Type, incidence, seriousness, nature, severity, and drug-relatedness of adverse events graded according to the National Cancer Institute Common Terminology Criteria for Adverse Events, Version 4.0 (NCI CTCAE v4.0)
- Changes in vital signs, physical findings, and clinical laboratory test results following study treatment administration

## 5.3 **Sample Size and Power**

**Dose Escalation:** The goal is to determine a dose level of CB-839 for which the rate of DLTs is less than 33%. A minimum of 9-12 patients are planned for Dose Escalation.

**Dose Expansion:** For Cohorts 1-5, Simon's two-stage design ([Simon 1989](#)) (3) will be used as outlined in [Table 1](#) below. The null hypothesis that the response rate is [ p0 ] will be tested against a one-sided alternative. In the first stage, [ n1 ] patients will be accrued. If there are [ r1 ] or fewer responses in these [ n1 ] patients, the study will be stopped. Otherwise, [ n - n1 ] additional patients will be accrued for a total of [ n ]. The null hypothesis will be rejected if [ r2 + 1 ] or more responses are observed in [ n ] patients. This design yields a type I error rate of 0.1 and power of 80% when the true response rate is [ p1 ].

**Table 1 Summary of Sample Size and Power for Expansion Cohorts**

Cohort	p0 (Background ORR (%))	p1 (Target ORR (%))	A	Power (%)	n1 for Stage 1 (r1)	n2 (n - n1) for Stage 2	Total n (r2)
1	25%	40%	0.1	80	25 (7)	27	52 (16)
2	5%	15%	0.1	80	20 (1)	36	56 (4)
3	5%	20%	0.1	80	9 (0)	15	24 (2)
4	5%	20%	0.1	80	9 (0)**	66	75 (13)
5	5%	15%	0.1	80	20 (1)	36	56 (4)
6	5%	20%	0.1	80	9 (0)	15	24 (2)

\*For all cohorts, false positive rate ( $\alpha$ ) = 0.1

\*\*Completed prior to protocol Amendment 2 expansion of cohort

### Expanded Cohort 4

A multi-stage design will be used as a guide for the melanoma expansion cohort 4 to decide whether the treatment of CB-839 in combination with nivolumab warrants more extensive development in this population. At first, a Simon 2-stage design ([Table 1](#)) with a reasonable false positive rate (eg, FPR < 10%) and false negative rate (eg, FNR < 20%) was used for the decision making based on assumptions of target (20%) and background (5%) response rate. Following a positive result in the initial two stage design and preliminary evidence of a treatment effect that may represent substantial improvement over available therapies, approximately 75 subjects in total will be treated in Cohort 4. The sample size at this expanded stage is determined based on the ability to produce a confidence interval (CI) that would exclude the historic response rate (assumed to be 10%) and to provide sufficient information for a reliable understanding of the safety profile. Specifically, the lower limit of the 95% CI associated with observation of an objective response rate of 18.7% in 75 treated subjects (14/75 responders) excludes 10%. Interim clinical monitoring will be performed in this expansion to ensure adequate safety and tolerability as well as favorable risk/benefit by assessing preliminary efficacy measures such as objective response rate and duration of response.

## 6 STUDY CONDUCT

### 6.1 Safety Data Monitoring

Safety data from the study is monitored on an ongoing basis via routine PrimeVigilance activities. In addition to real time medical review of emergent SAEs, a cross functional sponsor safety review team performs regular periodic aggregate data reviews across all CB-839 studies.

## 7 STATISTICAL METHODS

### 7.1 Analysis Sets

#### 7.1.1 Efficacy Evaluable Population for ORR– Response Evaluable Analysis Set

All patients who have measurable disease at baseline, receive at least one dose of study drug (CB-839 or nivolumab), and complete at least one post-baseline tumor assessment, will be considered evaluable for efficacy. In addition, patients who discontinue treatment for study-

drug related toxicity or for disease-related death also are included in the efficacy evaluable population for ORR.

All response efficacy analyses will be performed by cohort.

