## 6.3 Study Design

Protocol CX-839-004 is a Phase 1/2 open-label study of the combination of CB-839 with nivolumab in patients with advanced/metastatic ccRCC, MEL, and NSCLC, as well as CB-839 monotherapy in patients with advanced/metastatic MEL. Sequential dose escalation of CB-839 with full dose nivolumab (CB-Nivo) will take place in patients with advanced ccRCC,

advanced/metastatic MEL, or metastatic NSCLC. Subsequently, multiple disease-specific single-arm cohorts will be enrolled in which CB-839 will be administered in combination with the full approved dose of nivolumab. CB-839 will be administered at the RP2D established in dose escalation. Patients in dose escalation must be eligible for one of the dose expansion cohorts. CB-839 monotherapy will be administered at the previously established monotherapy RP2D of 800 mg PO BID.

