### 16.4.3 Response Evaluable Population

Patients treated in the protocol expansion phase or at the RP2D in the escalation phase who have measurable disease at baseline and complete at least one post-baseline tumor assessment, or discontinue study medication early due to study drug-related toxicity, or experience clinical disease progression will be considered evaluable for RECIST 1.1 response evaluation. Patients who discontinue study due to early disease-related death will be included in the response evaluable population if they received at least 21 days of treatment (approximately 42 doses of CB-839 and 2 doses of nivolumab). Patients who do not meet the aforementioned requirements will be considered non-evaluable for response and will be replaced.

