**Table S1 Comparison of RECIST v 1.1 and iRECIST****Protocol criteria for measurement of study endpoint****1. Definitions**

- 1.1 **Evaluable for adverse events.** All patients will be evaluable for adverse event evaluation from the time of their first treatment.
- 1.2 **Evaluable for response.** All patients who have received at least one cycle of therapy and have their disease re-evaluated will be considered evaluable for response (exceptions will be those who exhibit objective disease progression prior to the end of Cycle 1 who will also be considered evaluable). Patients on therapy for at least this period and who meet the other listed criteria will have their response classified according to the definitions set out below.

Response and progression will be evaluated in this study using the revised international criteria (1.1) proposed by the RECIST (Response Evaluation Criteria in Solid Tumors) committee as well as the modified iRECIST guidelines. Investigators should note the different requirements for confirmatory scans as well as follow up for the two criteria. See [Section 3.1.1](#) for criteria for continuing treatment past RECIST 1.1 disease progression.

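### SAP 7.1.1 defines the primary-ORR set differently from protocol 16.4.3, SAP 7.4.1 plans ORR on that set alone, and SAP 7.7 records neither

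*SAP*

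**What the plan says.** **Protocol 16.4.3** sets the scope as "Patients treated in the protocol expansion phase or at the RP2D in the escalation phase who have measurable disease at baseline". Such a patient qualifies with a post-baseline tumor assessment, or by stopping early for drug-related toxicity, or by a third route: "or experience clinical disease progression will be considered evaluable for RECIST 1.1 response evaluation". Early disease-related deaths are counted "if they received at least 21 days of treatment". Everyone else is non-evaluable and is replaced.

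**SAP 7.1.1** takes dosed patients with measurable disease who "complete at least one post-baseline tumor assessment, will be considered evaluable for efficacy". It then adds patients who stop treatment for "drug related toxicity or for disease-related death also are included in the efficacy evaluable population for ORR". It contains no clinical-progression route, no 21-day minimum, and no limit to expansion or RP2D patients.

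**SAP 7.4.1** analyses ORR on this set, with a Clopper-Pearson 95% interval, and counts patients without an assessed response as non-responders. **Protocol 16.1** says that efficacy is analysed on the evaluable population and also on all treated patients. **SAP 7.7** lists the Cohort 4 change from independent to investigator assessment, the removal of Cohort 6, the protocol-deviation summaries and the dropped iRECIST analyses. It does not mention the ORR set or the all-treated analysis.

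**The concern.** ORR is a primary efficacy endpoint in every cohort, and each cohort is single-arm, so the denominator rule is part of the result. A confirmed response needs two post-baseline assessments at least four weeks apart. A patient who progresses clinically before any scan is therefore a certain non-responder. The protocol counts that patient; the SAP does not. The SAP's non-responder rule does not help, because it applies within the set and this patient is outside it.

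The replacement rule adds a practical difficulty. The protocol fills each cohort by its own definition of evaluable, while the analysis uses the SAP's definition. The analysed number need not equal the planned 52, 56, 24 or 75.

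On dose, protocol 6.3 says "Patients in dose escalation must be eligible for one of the dose expansion cohorts". With the RP2D limit gone from SAP 7.1.1, nothing in that section says whether an escalation patient treated at another dose counts towards a cohort's ORR.

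SAP 7.7 does record other departures from the protocol, such as iRECIST. A reader would take its silence here to mean that the ORR set is unchanged.

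**Working it through.** **1. The plan's own figure.** Protocol 16.3 and SAP 5.3 state that the 95% interval for 14/75 excludes 10%. The Clopper-Pearson lower limit for x responders in n is the 2.5% quantile of a Beta(x, n − x + 1) distribution.

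- 14/75 = 18.67%; Beta(14, 62) gives 10.60% (upper limit 29.33%). The statement is reproduced.
- 13/75 = 17.33%; the lower limit is 9.57%. So 14 is the smallest count that meets the benchmark.

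**2. The two definitions side by side.**

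| Patient | Protocol 16.4.3 | SAP 7.1.1 | Effect of the SAP rule on ORR |
|---|---|---|---|
| Clinical progression, no post-baseline scan | in | out | can raise, never lower |
| Unscanned disease-related death, under 21 days of treatment | out | in | can lower, never raise |
| Escalation patient not at the RP2D | out | not excluded | either way |
| Stopped for drug-related toxicity, no scan | in | in | none |

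**3. Net direction.** Let the protocol set have N patients and R responders. Let a be the number of unscanned clinical progressors whom the SAP drops, and b the early deaths that it adds and the protocol does not already count. Both groups are non-responders. Leaving escalation aside,

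ORR by protocol = R/N; ORR by SAP = R/(N − a + b).

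With R above zero, the SAP figure is higher if a exceeds b and lower if b exceeds a. Neither count is in the documents, so the sign cannot be settled. If e escalation patients at other doses entered with s responders, the figure would be (R + s)/(N − a + b + e), which can move in either direction.

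**4. Scale per patient.** At the rejection boundaries in SAP Table 1, one patient dropped or added gives:

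| Cohort | Boundary | One dropped | One added |
|---|---|---|---|
| 1 | 17/52 = 32.69% | 17/51 = 33.33% | 17/53 = 32.08% |
| 2 and 5 | 5/56 = 8.93% | 5/55 = 9.09% | 5/57 = 8.77% |
| 3 | 3/24 = 12.50% | 3/23 = 13.04% | 3/25 = 12.00% |
| 4 | 14/75 = 18.67% | 14/74 = 18.92% | 14/76 = 18.42% |

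The shift is about 0.16 to 0.64 percentage points per patient.

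**5. Evaluable versus treated in Cohort 4: a separate question.** The benchmark in protocol 16.3 and SAP 5.3 refers to 75 treated subjects. Protocol 6.3.2.4 sets the target at about 75 response-evaluable patients. Assume that 75 evaluable patients are reached by replacement, that 14 respond, and that k further treated patients lie outside the set for any reason and did not respond.

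- k = 4: 14/79 = 17.72%, lower limit 10.04%.
- k = 5: 14/80 = 17.50%, lower limit 9.91%.

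From k = 5 (5/80 = 6.25% of treated patients), the evaluable-set interval excludes 10% and the all-treated interval does not. The value of k is an assumption.

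**The case against.** **The progressor group is small.** Protocol 10.5 requires a CT or MRI at end of treatment for anyone without a post-baseline image, and the SAP's own death clause catches some of the rest. This stands. It leaves clinical progressors who missed that scan and who did not stop for toxicity or disease-related death. The protocol itself provides a route for such patients.

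**The SAP inflates ORR.** A reader might infer this, but the documents do not support it. On early deaths the SAP is the more conservative document, and the net sign depends on counts that nobody has stated. Copying protocol 16.4.3 in full could remove non-responders whom the SAP now counts.

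**The mismatch could overturn the Cohort 4 conclusion.** The 14/80 figure does not show that. It compares evaluable with treated patients, and that gap exists under protocol 16.4.3 as well, because the protocol also excludes and replaces non-evaluable patients.

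**The all-treated result is hidden.** This goes too far. SAP 7.2 reports analysis populations by cohort for the safety set, which is all treated patients. Measurable disease is an entry criterion and a confirmed responder must have scans, so responders should already be in the evaluable set. A reader can largely derive the all-treated ORR as responders over the safety-set count. What is missing is a planned analysis with its interval.

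**Protocol 16.1 does not name ORR.** One could read it as satisfied by ORR on evaluable patients and PFS and OS on all treated patients. That reading is possible. The natural one is that both populations apply to efficacy generally, since no endpoint is exempted.

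**The SAP pools other doses.** It does not say so. It analyses by cohort, and SAP Section 5 describes expansion as enrolling at the RP2D. SAP 7.4 describes cohorts by tumor type, but that cannot be the literal definition because Cohorts 1 to 3 are all ccRCC. The fault is an omitted restriction.

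**A third definition.** Protocol Attachment 5, item 1.2, says "All patients who have received at least one cycle of therapy and have their disease re-evaluated will be considered evaluable for response", where the "exceptions will be those who exhibit objective disease progression prior to the end of Cycle 1". That attachment is sourced to the iRECIST guideline, and 16.4.3 is the operative statistical definition. The point does not rest on it.

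**Conclusion.** The point holds as a mismatch that should be fixed before analysis. SAP 7.1.1 differs from protocol 16.4.3 on clinical progression, early deaths and the expansion/RP2D limit. SAP 7.4.1 plans no all-treated ORR, and SAP 7.7 discloses none of this. Followed as written, the SAP removes certain non-responders from the denominator of a primary endpoint, and no other rule in it brings them back.

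The effect is probably modest: a fraction of a percentage point per patient in a group that the end-of-treatment scan keeps small. Its total size and net direction cannot be obtained from the documents. DOR is based on responders only, so the first two differences do not affect it.

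Two parts carry conditions. The all-treated limb rests on reading protocol 16.1 as covering ORR. The Cohort 4 illustration rests on an assumed number of treated non-responders outside the set; it shows why that benchmark needs a stated denominator, not what the mismatch does.

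**What to change.** - In SAP 7.1.1, restore the clinical-progression route and carry over the limit to expansion patients and escalation patients at the RP2D.
- For early disease-related deaths, either keep the SAP's inclusion of all of them and record it in SAP 7.7 as an intended departure, or reconcile it with the 21-day condition in 16.4.3. Keeping them is the more conservative choice for ORR.
- In SAP 7.4.1, add an all-treated ORR per cohort with a Clopper-Pearson 95% interval, counting patients without a post-baseline assessment as non-responders, beside the evaluable-set ORR.
- State whether the Cohort 4 benchmark of 14/75 is judged on treated or response-evaluable patients.
- Record in SAP 7.7 any remaining difference from the protocol.

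The cost is SAP wording and one extra table per cohort, with no new data collection. The all-treated ORR may be slightly lower than the evaluable-set ORR.
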